 - If a scan within the first 4 months exists and shows progressive disease the patient is not eligible (i.e. the scan result cannot be overruled by Investigator assessment of clinical benefit).
 - Should a subsequent scan for the same line of treatment show clinical benefit after initial radiographic progression (i.e. pseudoprogression) the patient is eligible.
- 27. Patients should have had only one CPI and one platinum based regimen, whether sequentially or concurrently. The acceptable sequences are:
 - Platinum-based chemotherapy (1L) + CPI treatment (1L); i.e., study treatment is second line therapy
 - Platinum-based chemotherapy (1L) → CPI treatment (2L); i.e., study treatment is third line therapy
 - CPI treatment (1L) → Platinum-based chemotherapy (2L); i.e., study treatment is third line therapy
 - Adjuvant chemo-radiation treatment with anti-PD-1/PD-L1 inhibitors or consolidation treatment with anti-PD-1/PD-L1 after definitive chemo-radiation therapy is allowed but participants do require an additional line of anti-PD-1/PD-L1 treatment in the metastatic setting.

Specific Inclusion Criteria for Part B3 Expansion in PD L1 High, CPI Naïve, First Line NSCLC Cohort

28. Participants with histologically confirmed advanced NSCLC with PD-L1 high defined as ≥ 50% PD-L1 expression based on immunohistochemistry using antibody clone 22c3, sp263 or 28-8. Expression will be determined in a fresh tumor biopsy collected during study screening or a possibly available archival sample, provided that the latter is not older than 12 months and has been obtained after failure of last CPI treatment line and prior to receiving study treatment.

Specific Inclusion Criteria for Part B4 Expansion in CPI-Naïve SCLC Cohort

- 29. Participants must have histologically confirmed SCLC.
- 30. Participants may have had prior chemotherapy, radiation therapy or declined approved therapies for SCLC.

Additional Inclusion Criteria for Part B5: CPI Naïve Esophageal Squamous Cell Carcinoma

- 31. Participants whose major lesion was histologically confirmed squamous cell carcinoma or adenosquamous cell carcinoma of the esophagus.
- 32. Patients who have previously received not more than 1 prior lines of treatment for metastatic disease prior to enrolling to the study. The prior line must be a fluoropyrimidine and platinum-based regimen and patients must have experienced progressive disease.

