4.1 OVERALL DESIGN

An overview of the study design is provided in Section 1.2.

Study NP40435 is a first-in-human, open-label, multicenter, Phase I multiple-ascending dose (MAD) study of single agent RO7121661. The study consists of 2 parts (A and B):

- Part A (RO7121661 Dose Escalation): To determine the MTD and/or RDE based on safety, tolerability, PK, and/or the PD profile of escalating doses of RO7121661 every 2 weeks (Q2W). If for specific cleared cohort(s) the safety, PK and/or RO and/or the biomarker profile need to be further characterized, additional participants, potentially enriched in certain indications and/or characteristics, may be enrolled.
- Part B (RO7121661 Tumor-Specific Expansion Cohorts): To evaluate anti-tumor activity of the RDE of RO7121661 from Part A (2.1 g Q2W) and to confirm safety and tolerability in participants with selected tumor types. B1, B2, B4 and B5 expansions may be staggered, sequential or concurrent. Part B3 will not proceed prior to generation of data from the initial CPI experienced indication(s):
 - Part B1: CPI experienced second line and beyond metastatic melanoma
 - Part B2: CPI and platinum experienced second or third line PD-L1 positive NSCLC
 - Part B3: PD-L1 positive, CPI naïve, first line NSCLC
 - Part B4: CPI-naïve SCLC with prior failure of, progression on, or intolerance to standard therapy
 - Part B5: CPI-naïve ESCC

Part A of the study will enroll participants with solid tumors who have progressed on a cancer therapy or who are not amenable to standard of care. At least DLT evaluable participants will be enrolled in each cohort during the dose escalation (see Section 4.1.3). Dose escalation will be carried out according to a modified continual reassessment method (mCRM) with escalation with overdose control (EWOC) design, with the aim of identifying the MTD/RDE of RO7121661.

Since RO7121661 will be administered Q2W in Part A, the cycle length will be defined as 14 days. The maximum total number of participants in the dose escalation portions of Part A1 will be approximately DLT evaluable participants on a Q2W schedule. A dose cohort can be extended to enroll additional participants (approximately), potentially enriched in certain tumor types and/or characteristics to confirm safety, PK and/or RO and/or the biomarker profile.

Part B1 and/or B2 and/or B4 and/or B5 may commence upon completion of Part A. The starting dose of RO7121661 for Part B is 2.1 g Q2W as derived from the RDE in Part A

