determined by safety, PK and/or RO and/or the biomarker profile. Part B3 will not proceed prior to generation of data from the initial CPI experienced indication(s).

Patients enrolled in Part B expansions have more specific limitations of prior therapies for inclusion than during the dose escalation. Patients enrolled in Part B1 (CPI experienced melanoma) must have had treatment with approved anti-PD-L1/anti-PD-1 checkpoint inhibitors. Patients enrolled in Part B2 (CPI and platinum experienced, PD-L1 expression \geq 1% NSCLC) must have had a checkpoint inhibitor and platinum chemotherapy. Patients enrolled in Part B3 (untreated, CIT naïve NSCLC with PD-L1 expression \geq 50%) should not have had any prior therapy. Patients enrolled in Part B4 (CPI naïve SCLC) and B5 (CPI-naïve ESCC) should not have had any prior checkpoint inhibitor therapy but may have had chemotherapy. Specific details for Part B Expansions are included in the Inclusion and Exclusion Criteria (Section 5.1 and Section 5.2).

In Part B (tumor specific expansion cohorts) approximately participants will be included per indication. Part B cohorts may run in parallel, staggered or sequentially.

Participants will be treated with RO7121661 until disease progression, unacceptable toxicities, or withdrawal of consent. Participants may continue treatment with RO7121661 (Part A and B) for 24 months or longer if the participant is still benefitting from treatment at the time of the last visit at the end of the two-year period. As with other immunotherapies, treatment beyond progressive disease according to RECIST Version 1.1 can be considered after consultation and agreement between the Sponsor and Investigator.

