5. STUDY POPULATION

The study population rationale is provided in Section 4.3.1.

The study population consists of male and female participants with advanced and/or metastatic solid tumors.

Prospective approval of protocol deviations from recruitment and enrollment criteria, also known as protocol waivers or exemptions, is not permitted.

Participants enrolled in the study but who do not maintain eligibility or withdraw consent **prior to the first dose** will not be included in the database.

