 - Adjuvant chemo-radiation treatment with anti-PD-1/PD-L1 inhibitors or consolidation treatment with anti-PD-1/PD-L1 inhibitors after definitive chemo-radiation therapy is allowed but participants do require an additional line of anti-PD-1/PD-L1 treatment in the metastatic setting.

Specific Inclusion Criteria for Part B3 Expansion in PD L1 High, CPI Naïve, First **Line NSCLC Cohort**

28. Participants with histologically confirmed advanced NSCLC with PD-L1 high defined as ≥ 50% PD-L1 expression based on immunohistochemistry using antibody clone 22c3, sp263, or 28-8. Expression will be determined in a fresh tumor biopsy collected during study screening or a possibly available archival sample, provided that the latter is not older than 12 months and has been obtained after failure of last CPI treatment line and prior to receiving study treatment.

Specific Inclusion Criteria for Part B4 Expansion in CPI-Naïve SCLC Cohort

- 29. Participants must have histologically confirmed SCLC.
- 30. Participants may have had prior chemotherapy, radiation therapy or declined approved therapies for SCLC.

Additional Specific Inclusion Criteria for Part B5: CPI Naïve Esophageal **Squamous Cell Carcinoma**

- 31. Participants whose major lesion was histologically confirmed squamous cell carcinoma or adenosquamous cell carcinoma of the esophagus.
- 32. Patients who have previously received not more than 1 prior lines of treatment for metastatic disease prior to enrolling to the study. The prior line must be a fluoropyrimidine and platinum-based regimen and patients must have experienced progressive disease.
- 33. Patients who underwent a radical resection (R0 resection confirmed) in conjunction with chemotherapy with fluoropyrimidine and platinum-based drugs including neoadjuvant/adjuvant therapy and chemo-radiation (including patients who underwent chemo-radiation followed by salvage surgery) are allowed.
 - If recurrence was confirmed by imaging within 24 weeks after the last dose of the treatment, the therapy should be counted as equivalent to metastatic treatment. Such patients are eligible and do not require an additional line of therapy in the metastatic setting.

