
Specific Exclusion Criteria for Part B3 Expansion (1st line CIT naïve patients)

- 29. Prior therapy for metastatic disease is not permitted i.e., treatment with any immune CPIs (such as anti-PD-L1/PD-1, CTLA-4), immunomodulatory mAbs, other immunomodulator therapies, chemotherapy or TKIs.
- 30. Adjuvant anti-PD-1 or anti-PD-L1 therapy is not allowed. Adjuvant chemotherapy is permitted as long as treatment was administered > 6 months prior to Cycle 1, Day 1.

Specific Exclusion Criteria for NSCLC patients (Part B2)

31. NSCLC patients with the following mutations, rearrangements, translocations are not eligible for Part B2: EGFR; ALK; ROS1, BRAFV600E, NTRK

Specific Exclusion Criteria for Part B4 Expansion (CPI-naïve SCLC patients)

32. Prior therapy with any immune CPIs (such as anti-PD-L1/PD-1, anti-CTLA-4), is not permitted.

Specific Exclusion Criteria for Part B5: CPI Naïve Esophageal Squamous Cell Carcinoma

33. Prior therapy with any immunomodulatory agents including CPIs (such as anti-PD-L1/PD-1, anti-CTLA-4), is not permitted.

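### The archival-tissue condition for Part B3 PD-L1 testing (inclusion criterion 28) is carried over from Part B2 and, read literally, cannot be met in a CPI-naïve cohort

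*Combined protocol and SAP*

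**What the plan says.** Criterion 28 (Section 5.1) requires at least 50% PD-L1 expression for Part B3. It names two tissue sources: a fresh biopsy taken during screening, or an archival sample "provided that the latter is not older than 12 months and has been obtained after failure of last CPI treatment line". The synopsis repeats the condition: "has been obtained after failure of last CPI treatment line and prior to receiving study treatment". Criterion 25, for Part B2, uses the same wording.

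Section 4.1 describes the cohort as "Part B3: PD-L1 positive, CPI naïve, first line NSCLC" and says that its patients "should not have had any prior therapy". In Section 5.2, exclusion 29 states "Prior therapy for metastatic disease is not permitted i.e., treatment with any immune CPIs" and exclusion 30 states "Adjuvant anti-PD-1 or anti-PD-L1 therapy is not allowed". Exclusion 30 does allow adjuvant chemotherapy, "permitted as long as treatment was administered > 6 months prior to Cycle 1, Day 1". Section 5 adds: "Prospective approval of protocol deviations from recruitment and enrollment criteria, also known as protocol waivers or exemptions, is not permitted".

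**The concern.** The condition makes sense in B2. Criterion 24 requires earlier PD-1 or PD-L1 inhibitor treatment there, and tissue taken after that treatment failed reflects the tumor as it now is. In B3 the event that the condition refers to has not happened in any eligible patient. The plan offers an archival route and then attaches a requirement that closes it.

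Two things are at stake. The first is whether PD-L1 eligibility can be established for a B3 patient who has usable archival tissue but cannot readily be biopsied. The second is consistency: a literal reader rejects all archival tissue, while a reader who ignores the clause accepts any sample within 12 months. No error rate, sample size or analysis is involved.

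**Working it through.** No arithmetic applies and the plan gives no figure to reproduce. The check sets the passages against one another.

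1. **Condition.** Criterion 28 asks three things of an archival sample: it is no more than 12 months old, it was taken after the last CPI line failed, and it was taken before study treatment. The second presupposes at least one earlier CPI line.

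2. **Does any eligible B3 patient have such a line?** Exclusion 29 rules out CPI for metastatic disease. Exclusion 30 rules out adjuvant PD-1 or PD-L1 inhibitors. The cohort definition in Section 4.1 and the heading above criterion 28 cover any other setting, because both say CPI-naïve, and Section 5.1 defines CPI-experienced as any earlier PD-1 or PD-L1 inhibitor treatment. The adjuvant chemotherapy that exclusion 30 tolerates is not a CPI and does not supply the missing line. The answer is no.

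3. **Is there an exemption?** Neither copy of criterion 28 limits the clause to patients with earlier CPI treatment, and no other section exempts B3.

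4. **Comparison with B2.** Criteria 25 and 28 differ in the expression threshold (1% against 50%) but not in the archival condition. That fits a clause carried from one cohort to the other. Because it stands in both the synopsis and Section 5.1, both copies need correcting.

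5. **Which routes remain?**
   - Fresh biopsy: Section 8.6.2.2 makes screening biopsies mandatory in all Part B cohorts and mentions B3 as a cohort in which one may be needed to confirm PD-L1.
   - Existing biopsies: the same section lets recent diagnostic tissue be discussed with the Sponsor, provided no tumor treatment followed it. It does not say that such tissue satisfies criterion 28.
   - Procedures before consent: Sections 8 and 8.10.1 allow routine procedures and tests to count within the screening window. They do not mention archival tissue, and Section 8 requires that the protocol's own criteria be met.

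6. **Who is affected?**
   - Criterion 17 lets a Part B patient with a single target lesion and no other lesion that can be biopsied go without biopsies. For that patient archival tissue is the natural PD-L1 source. Biopsying the single lesion may conflict with criterion 15, which requires a measurable lesion that is not intended for biopsy.
   - A candidate with suitable archival tissue but expression below 50% would have a fresh biopsy only to be found ineligible.
   - Most other B3 candidates would have a baseline biopsy anyway, so for them the clause mainly changes whether it comes before or after PD-L1 status is known.

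**The case against.** The best case against the point has four parts.

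- **The clause can be read as not applicable.** Where no CPI line exists, a sensible site may disregard it, and doing so is arguably interpretation and not a waiver. This is a possible reading, and for that reason the claim is limited to the literal text. The protocol does not state that reading, and Section 5 leaves little room for sites to relax an enrollment criterion.
- **Fresh biopsy is the default.** This stands. A reader might infer that B3 cannot enroll or that its PD-L1 status cannot be determined. The documents do not support that, because criterion 28 itself offers the fresh-biopsy route.
- **The Sponsor would catch the problem.** Section 4.1.5 has the Sponsor review and approve each pre-screened Part B patient for the proposed cohort. This makes divergent practice between sites less likely, but it does not tell anyone which reading applies.
- **B3 may never open.** Section 4.3.1 makes the cohort conditional on support from B1 and/or B2. This limits the practical reach of the clause but does not make the text right.

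A reader might also try to size the problem by comparing the 28-day screening window with the 12-month tissue limit. That ratio compares calendar periods and says nothing about patients or samples, so it is no measure of the effect.

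**Conclusion.** The point holds as a minor internal inconsistency. Taken literally, criterion 28 disables the archival route for B3, in both places where it appears. That conclusion is textual and rests on no numerical assumption, only on reading the clause as a requirement on every archival B3 sample.

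The consequence is narrow. B3 patients excused from biopsy under criterion 17 could lose their PD-L1 source, and some candidates could have a biopsy that serves only to show they are ineligible. How many is unknown, since the documents give neither archival-tissue availability nor the frequency of biopsy omission.

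**What to change.** In criterion 28, in Section 5.1 and in the synopsis, delete the condition that the archival sample follow failure of the last CPI line. Two requirements then remain: the sample is no more than 12 months old, and it was obtained before study treatment. The verb has to be supplied again so that the sentence still reads. Leave criterion 25 unchanged, because the condition fits B2.

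Whether B3 archival tissue should also be free of intervening tumor treatment, as Section 8.6.2.2 asks of existing biopsies, is a separate decision for the sponsor. There is a reason to consider it: exclusion 30 permits adjuvant chemotherapy more than 6 months before Day 1, so tissue between about 6 and 12 months old could predate it. It would, however, be a new eligibility rule that could bar otherwise acceptable tissue, and this correction does not need it.

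The cost is the same short deletion in two places, with no change to sample size, visits or analysis.

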Pembrolizumab has also received approval for treatment-naïve patients with advanced NSCLC without driver mutations and with tumor proportion score (TPS) ≥50% or high tumor PD-L1 expression, based on the KEYNOTE-024 Phase III study (Reck et al 2016). Pembrolizumab also received accelerated approval in combination with platinum and pemetrexed in first line treatment-naïve non-squamous patients irrespective of PD-L1 status based on Phase II results in KEYNOTE-021 (Langer et al 2016) and confirmed in the Phase III KEYNOTE-189 study (Gandhi et al 2018). Recent results from CheckMate 227, a Phase III trial in patients with chemotherapy-naïve stage IV or recurrent NSCLC demonstrates improvement in PFS with first-line nivolumab plus ipilimumab than with chemotherapy among patients with a high tumor mutational burden (TMB), irrespective of PD-L1 expression level. (Hellmann et al 2018) supporting a potential role for the use of TMB as a selection marker for treatment. Furthermore, durvalumab was approved for patients with unresectable Stage III NSCLC based on Phase III results in the PACIFIC study (Antonia et al 2017).

2.2.2 Small Cell Lung Cancer Patients: Checkpoint Inhibitor Naïve

In 2012, the World Health Organization (WHO) estimated the worldwide incidence of new lung cancer cases was 1.8 million, resulting in approximately 1.6 million deaths and accounting for about 13% of total cancer diagnoses (Ferlay et al 2012). In the Western World, approximately 13% of the lung cancers that are diagnosed are small cell lung cancer (SCLC). SCLC occurs primarily in patients with a history of tobacco use and originates from neuroendocrine cell precursors. It is characterized by rapid growth, high response rates to both chemotherapy and radiotherapy, and the development of treatment resistance in patients with metastatic disease (Früh et al 2013).

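### B3 is meant to be CPI naïve, but no numbered B3 criterion bars a patient given PD-L1 consolidation after chemoradiation for stage III NSCLC

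*Combined protocol and SAP*

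**What the plan says.** Section 4.1 lists the cohort as "Part B3: PD-L1 positive, CPI naïve, first line NSCLC". It calls these patients untreated and CIT naïve and says they "should not have had any prior therapy". Section 4.3.1 describes them as naïve to both CIT and chemotherapy. The headings over inclusion 28 and over exclusions 29-30 also label the cohort naïve.

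The numbered criteria in Section 5.2 read differently. Exclusion 29 begins "Prior therapy for metastatic disease is not permitted i.e., treatment with any immune CPIs" and goes on to list other agent classes. Exclusion 30 states that "Adjuvant anti-PD-1 or anti-PD-L1 therapy is not allowed", and permits adjuvant chemotherapy given more than 6 months before Cycle 1, Day 1.

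For B4, exclusion 32 is not tied to any setting: "Prior therapy with any immune CPIs (such as anti-PD-L1/PD-1, anti-CTLA-4), is not permitted". Exclusion 33 does the same for B5 and extends to other immunomodulatory agents.

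Two further passages show that the protocol knows the setting at issue. Section 2.2.1 records that "durvalumab was approved for patients with unresectable Stage III NSCLC". For B2, inclusion 27 names adjuvant chemo-radiation with a PD-1/PD-L1 inhibitor and then, as a separate item, says that "consolidation treatment with anti-PD-1/PD-L1 inhibitors after definitive chemo-radiation therapy is allowed".

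**The concern.** Both B3 exclusions are tied to a setting, metastatic or adjuvant. Consolidation PD-L1 therapy after definitive chemoradiation for stage III disease is neither in the protocol's own usage. A patient who is CPI experienced under the Section 5.1 definition could therefore satisfy every numbered B3 criterion.

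Two things are at stake. First, interpretation: ORR, DCR, DoR and PFS are primary endpoints for the expansion part (Table 4). Section 4.3.1 justifies B3 by the hope of added TIM-3 activity in the patients thought most likely to respond to PD-1 therapy. Section 9.5 foresees that later interim looks may set observed activity against what standard of care would be expected to give. CPI-pretreated patients in B3 would mix two populations in those summaries.

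Second, safety screening: exclusions 26-28 deal with earlier immune-mediated events that were Grade 4, ended the prior immunotherapy or have not resolved. They apply only to B1 and B2, so a pretreated patient who entered B3 would not be checked against them.

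**Working it through.** No sample size, power or event count is involved, so the check sets the criteria side by side.

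| Prior anti-PD-1/PD-L1 given as | B3 | B4 | B5 |
|---|---|---|---|
| Therapy for metastatic disease | barred, exclusion 29 | barred, exclusion 32 | barred, exclusion 33 |
| Adjuvant therapy | barred, exclusion 30 | barred, exclusion 32 | barred, exclusion 33 |
| Consolidation after definitive chemoradiation | not named | barred, exclusion 32 | barred, exclusion 33 |

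Take a test patient with stage III NSCLC who had definitive chemoradiation and PD-L1 consolidation, progressed to advanced disease while on consolidation, has PD-L1 expression of at least 50%, and has completed the washouts.

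1. **Exclusion 29.** The full lead-in is "Prior therapy for metastatic disease is not permitted i.e., treatment with any immune CPIs (such as anti-PD-L1/PD-1, CTLA-4), immunomodulatory mAbs". The list follows an i.e., so it spells out what counts as therapy for metastatic disease. Stage III treatment is not that. Inclusion 27 agrees: for B2, a patient who had consolidation still needs a further anti-PD-1/PD-L1 line in the metastatic setting. Not triggered.
2. **Exclusion 30.** Inclusion 27 names adjuvant and consolidation use separately, so adjuvant does not clearly cover consolidation. Not triggered.
3. **Inclusion 28.** It sets histology, PD-L1 level and sample rules, with no CPI-naïve condition in its text. Its archival-sample rule in fact asks for tissue taken after the last CPI line failed. Inclusion 25 uses the same rule for the CPI-experienced B2 cohort, and it makes no sense for a naïve patient.
4. **General prior-therapy exclusions 18-25.** Exclusion 19 says where prior CPIs are allowed (Part A, B1, B2) and is silent on B3. Exclusion 20 bars TIM-3 inhibitors. The rest concern vaccines, investigational drugs, immunosuppressants, steroids, radiotherapy and transfusion. None bars an approved PD-L1 inhibitor given earlier.
5. **Inclusions 18-20**, which Section 5.1 applies to CPI-experienced participants in Part B. They require progression on the agent and accept prior use as indicated, other than adjuvant. The test patient meets them. They might stop someone who relapsed after completing consolidation, but they do not require CPI-naïve status.
6. **Section 5.1 definition.** Prior treatment with an anti-PD-1 or anti-PD-L1 agent makes the patient CPI experienced. The test patient is therefore outside the intended B3 population.

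Steps 1-5 do not exclude the patient; step 6 says that the patient does not belong. That is the mismatch.

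**The case against.** The strongest reply is that the intended population is stated repeatedly: in the cohort list, the design text, Section 4.3.1 and two headings. Together with the Section 5.1 definition, these leave little doubt that a pretreated patient is not wanted. Exclusion 19 omits B3 from the parts where prior CPI is allowed. Under Section 4.1.5 the sponsor reviews and approves each pre-screened Part B participant for the proposed cohort, so someone would have to approve a CPI-experienced patient for a CPI-naïve cohort. It is also fair to say that exclusion 30's allowance for chemotherapy is no allowance for CPIs.

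All of this stands as evidence of intent and lowers the chance of the error. It does not supply the missing criterion. Section 4.1 sends the reader to Sections 5.1 and 5.2 for the specific rules, exclusion 19 is silent on B3 and does not prohibit, and the sponsor's approval is a review step with no stated criterion on this point.

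Four stronger readings are tempting and are not supported:

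- **That the sponsor means to admit these patients.** The labels and design text say the opposite.
- **That B3 has no minimum interval after chemoradiation.** Section 6.5.2 requires 28 days or 5 half-lives, whichever is shorter, for chemotherapy and immunotherapy. Exclusion 24 requires 4 weeks for radiotherapy, limited palliative treatment excepted. Only the 6-month interval is confined to adjuvant chemotherapy.
- **That these patients belong in B2.** Inclusion 27 refuses a patient whose only CPI was consolidation, and B2 also refuses platinum-only patients because it requires a CPI.
- **That the loss in B3 response rate can be put in percentage points.** It would equal the share of pretreated patients times the difference in response rate between naïve and pretreated patients. The documents give neither factor, and the cohort size is blacked out.

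**Conclusion.** The concern holds as an internal inconsistency: B3 is defined as CPI naïve, but its numbered exclusions leave out one recognised setting of prior PD-L1 therapy that B4 and B5 cover. It rests on two readings of the text: that the list in exclusion 29 explains its lead clause, and that adjuvant in exclusion 30 does not include consolidation. Inclusion 27 supports both.

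The consequence is possible entry of the wrong population into a cohort with primary activity endpoints, without the immune-mediated-event screen used for other pretreated patients. How many patients this would affect is unknown. B3 has no formal hypothesis or power basis (Sections 9.1 and 9.2) and ORR is descriptive with a 90% interval (Section 9.4.2), so no error rate is affected. The point should be corrected because the repair is cheap and matches the sponsor's stated intent.

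**What to change.** Add to the B3 exclusions the bar already used for B4 in exclusion 32: "Prior therapy with any immune CPIs (such as anti-PD-L1/PD-1, anti-CTLA-4), is not permitted". Make the same change in the synopsis, which repeats the B3 wording. In inclusion 28 and its synopsis copy, correct the archival-sample phrase that presupposes a failed CPI line.

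Separately, reconcile how earlier adjuvant chemotherapy and definitive chemoradiation count. Exclusion 30 permits the former after an interval and does not address the latter. Section 4.1 says no prior therapy at all, and Section 4.3.1 says chemotherapy naïve. The sponsor should decide the rule and state it identically in all of these places; this review does not propose one.

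The cost is a wording amendment. The small downside is that a few patients relapsing after stage III treatment with PD-L1 consolidation become expressly ineligible for B3.
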